## **4 STUDY OBJECTIVES AND OUTCOME MEASURES**

## 4.1 Primary Endpoints

1. Safety: The primary endpoint will be the percentage of subjects reporting severe (CTCAE v5.0 grade  $\geq$ 3) adverse event (AE) or serious adverse event (SAE), when treated with sirolimus (TAVT-18). Additional safety-related endpoints include:

- a. Percentage of subjects that reduce or discontinue treatment due to an AE or SAE (any grade).
- b. Number of days treatment is withheld due to an AE or SAE (any grade).

2. *Efficacy*: The primary endpoint for efficacy will be time to seizure onset, when treated with sirolimus (TAVT-18). Additional efficacy-related endpoints include:

- a. Age at time of seizure onset
- b. Percentage of subjects with infantile spasms (past or current) at the end of the treatment period (12 months of age).
- c. Seizure frequency at the end of the treatment period (12 months of age).

## 4.2 Secondary Endpoints

1. To evaluate the effect of early sirolimus (TAVT-18) treatment in TSC infants on epilepsyassociated neurodevelopment outcomes using the TSC-associated Neuropsychiatric Disorders (TAND) Checklist, Vineland Adaptive Behavioral Scales (VABS), Bayley Scales of Infant and Toddler Development (Bayley-4), Preschool Language Scale, Fifth Edition (PLS-5), and Autism Diagnostic Observation Schedule, Second Edition (ADOS-2). 2. To evaluate the effect of early sirolimus (TAVT-18) treatment in TSC infants on electrophysiological biomarkers of neuronal connectivity with EEG, we will measure frequency of interictal and ictal epileptiform activity, mean coherence, average path length, clustering coefficient, and global efficiency. We also will explore if these EEG biomarkers of functional connectivity correlate with white matter tracts associated with neurodevelopmental and/or neurocognitive impairment in TSC and treatment with mTOR inhibitors in TSC.

3. To develop a predictive dosing model for early sirolimus (TAVT-18) treatment in TSC infants using TAVT-18, we will measure steady-state blood trough concentration (ng/mL) corresponding to actual and dose-normalized sirolimus dose (mg/m^2/day).

## **5 STUDY DESIGN AND ORGANIZATION**

This trial originally planned to use a two stage, phase I clinical trial design, with the first stage to employ an open-label clinical trial design to verify dosing for TAVT-18 (sirolimus) powder for oral solution in TSC infants (N=5) that would then be carried forward to inform appropriate initial dosing, dosing frequency, and dosing adjustments for the second stage—a randomized, double-blind, placebo-controlled multi-site trial design—to evaluate the safety and efficacy of early sirolimus treatment to prevent epilepsy in TSC infants until 12 months of age (N=60). However, with the elimination of the planned second stage which has now been replaced by STOP2B: TSC-STEPS, the study design now consists of a single stage, phase I clinical trial design only. Subjects will be between 0-6 months of age at time of treatment initiation and meet clinical and/or genetic diagnostic criteria for TSC and have no prior history of clinical seizures at time of enrollment. Treatment will be continued until subjects reach 12 months of age. The TSC Clinic at Cincinnati Children's Hospital Medical Center (CCHMC) will serve as the single clinical site.

Additional key investigators of the study:

- [name] (CCHMC) will direct EEG acquisition and data transfer quality control, processing, and blinded central analysis
- [name] (UNC, Chapel Hill) will direct neuropsychological assessments and data transfer quality control, processing, and blinded central analysis
- [name] [name] (CCHMC) will direct PK/PD sample acquisition and quality control, processing, and blinded central analysis
- [name] (Boston Children's Hospital) will direct dMRI acquisition and data transfer quality control, processing, and blinded central analysis
- [name] (CCHMC) will serve as study biostatistician

Operations will be managed through the Clinical Coordinating Center (CCC) and Data Management Center (DMC) at CCHMC to ensure the optimal scientific rigor, efficient execution and management of the study, and analyses.

An independent medical monitor (MM) and Data Safety Monitoring Board (DSMB) will be established to ensure patient safety is appropriately monitored and prioritized throughout the study.

## **6 BENEFITS AND RISKS**

#### 6.1 Risk and Benefit Analysis

This study is greater than minimal risk, but with the potential for direct benefit.

### **6.2 Potential Benefits**

#### Potential Benefits to Subjects and Others

There may be some benefit to research subjects from the therapeutic intervention and evaluations as part of this research. When available and as long as disclosure does not have the potential to impact the accuracy of future assessments of the subject during the course of the study, results of research-specific procedures and assessments performed during the course of this study may be provided to parents and clinicians.

#### Importance of the Knowledge to be Gained

The most important information to be gained from this research will be the possibility of developing a targeted, disease-modifying drug therapy to prevent seizure onset and epilepsy progression in infants with TSC.

#### 6.3 Potential Risks

EEGs are routine clinical tests that are considered safe and carry negligible risk. EEGs have a minor risk of skin irritation due to adhesive used for sensor attachment but are routinely performed as part of clinical care for subjects with TSC in this age group.

MRIs are routine clinical tests that are considered safe and carry negligible risk. For subjects with TSC in this age group, the MRI performed yearly as part of clinical care routinely includes sedation. This sedation will be extended during the research portion of the MRI for no more than 15 minutes.

For blood sample collection to measure sirolimus levels and laboratory studies, there is a minor risk of pain, bleeding, bruising, or infection. When possible, blood draws will be combined with venipuncture already being performed for clinical purposes.

As part of this study there is a minor risk for a loss of confidentiality. Good clinical practice standards and institutional rules will be observed throughout all aspects of the study to maintain subject confidentiality. No individually identifiable subject data will be distributed to non-research personnel.

## 7 STUDY DURATION

The trial is for 3 years. Subject recruitment will occur during year 1 and completion of scheduled clinical visits and data analysis will occur in years 2-3.

## **8 SELECTION AND WITHDRAWAL OF SUBJECTS**

Evaluable subjects are those who have initiated treatment with sirolimus, complete the initial

Version: 7.0\_11May2022

follow-up visit 1 month after initiating treatment, and complete the final assessment at 12 months of age.

Male and female TSC infants 0-6 months of age will be enrolled. There will be no exclusion based on race or sex.

Subjects will be recruited through the TSC clinics which are geographically distributed to allow nationwide recruitment, supplemented by and in partnership with the advocacy organization Tuberous Sclerosis Alliance (TS Alliance) website, *Perspective* magazine, and social media efforts (Facebook and Inspire, online community support page). We will continue existing strategies to improve recruitment and retention that have been successful in our TACERN and PREVeNT studies of TSC infants, which have been able to recruit a similar number of TSC infants under 12 months of age over a similar time period proposed for the current study. Successful recruitment strategies utilized in the past and continued here include leveraging existing outreach and clinical support programs at each center, financial support when available for qualified travel expenses, scheduling visit times and places that accommodate the needs of the family, providing regular feedback to families about the ongoing progress of their children, and optimization of overall TSC clinical medical care.

We may modify recruitment strategies as needed if the current pandemic or other events affect the ability for subjects to travel or willingness to be seen at a research site on schedule or if protocol-required assessments/procedures cannot be performed in a validated manner. Telehealth for clinical assessment of subjects, local collection of sirolimus levels and safety laboratory studies, and increased use of parent-reported measures or personal protective equipment/physical distancing-friendly tools are such strategies in current use by other TSC studies during the COVID-19 pandemic.

## 8.1 Inclusion Criteria

- 0-6 months of age at the time of enrollment (subject must be <7 months of chronological age at time of randomization and treatment initiation). Corrected age must be at least 39 weeks (calculated by subtracting the number of weeks born before 40 weeks gestation from the chronological age).
- 2. Has a confirmed diagnosis of TSC based on established clinical or genetic criteria

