## 9 STUDY TREATMENT AND DOSING

## 9.1 STUDY MEDICATION (TAVT-18 SIROLIMUS)

The half-life of sirolimus (TAVT-18) is estimated to be >30 hours, allowing for convenient twice daily oral dosing. Medication should be taken in the fed state, defined as within 30 minutes of feeding. An individualized PK model-informed age-adjusted dosing scheme with a starting dose based on age at the time of enrollment (see Table 2) will be utilized, which is based on previous experience and simulation analysis of data obtained from our previous studies treating infants with congenital vascular anomalies with RapamuneTM 49, 77, 82 and preclinical and human studies with TAVT-18. These targeted doses are estimated based on the assumption that the oral bioavailability of TAVT-18 is 2-times higher compared to RapamuneTM. The target pre-dose whole blood trough sirolimus concentration (Cmin) will be 10 ng/mL with an upper tolerance range of 10-15 ng/mL. This target is consistent with prior published experience from infants treated with sirolimus for clinical indications and previous clinical trials in TSC patients treated for SEGA or epilepsy.

Table 2: Estimated	l sirolimus (TAVT-18) starting doses for the indicated target
concentration rang	ge 
Age group	Dosing for target concentration range = 10-15 ng/ml

(months)	
0-1	$0.2 \text{ mg/m}^2/\text{dose}$ , administered twice daily (total daily dose = $0.4 \text{ mg/m}^2$ )
1-2	$0.25 \text{ mg/m}^2/\text{dose}$ , administered twice daily (total daily dose = $0.5 \text{ mg/m}^2$ )
2-3	$0.3 \text{ mg/m}^2/\text{dose}$ , administered twice daily (total daily dose = $0.6 \text{ mg/m}^2$ )
3-4	$0.35 \text{ mg/m}^2/\text{dose}$ , administered twice daily (total daily dose = $0.7 \text{ mg/m}^2$ )

4-6	$0.45 \text{ mg/m}^2/\text{dose}$ , administered twice daily (total daily dose = 0.9 mg/m 	5

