## 11.3 Interim Analysis and DSMB Determination of Study Continuation

After the last (5th) subject completes the 14-day open-label treatment study visit, a detailed PKdosing and preliminary safety analysis report will be prepared by the study team for review by the study sponsor, drug supplier, and DSMB. Specific criteria for continuation of the study (Go/No-Go criteria) are not specified for this Phase I study, but the report must address the following key questions to the DSMB's satisfaction:

- (1) Is 0.2-0.45 mg/m^2 TAVT-18 (sirolimus) dosed orally 2x/day appropriate for initial dosing in TSC infants 0-6 months of age to achieve a target sirolimus trough levels between 5-15 ng/ml?
- (2) Does the proposed real-time, individualized PK model-based precision-dosing strategy for TAVT-18 (sirolimus) in TSC infants perform adequately in order achieve the target steady-state sirolimus trough level of 10 ng/ml?

- (3) Are there any unique safety events or related concerns that have emerged in TSC infants that were not anticipated which significantly alter the potential benefit-to-risk profile for TAVT-18 (sirolimus) in this population?
- (4) Have any practical issues with the planned study design been identified which were not anticipated that could impact the feasibility or successful completion of the primary objectives of the study?

The DSMB may request additional information or analysis from the investigators, modification to the study design, or study discontinuation.

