## Baseline Visit (Screening/Treatment Initiation)

To be eligible, infants 0-6 months of age must have a confirmed diagnosis of TSC based on established clinical and/or genetic criteria. During the baseline visit, eligibility criteria will be verified, baseline medical history/demographics, vital signs, and any existing laboratory or diagnostic testing results will be collected. A clinical examination along with a routine video-EEG and safety laboratory tests (with option for additional blood samples to be collected at the same time and stored at the TSC Biorepository located at the Van Andel Research Institute for future genetic and/or molecular studies) will be performed. Dispensation of study drug will occur following confirmation of eligibility. Genetic mutation information will be collected, but genetic testing will not be required to be positive if clinical criteria are fulfilled since up to 15% of subjects will clinically-definite TSC have no mutation identified through conventional genetic testing.

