#### **TABLE 3: Schedule of Study Procedures/Events**

Neuropsych assessment 						Х	Х
Dispense Study Drug	Х	Х	Х	Х	Х		
Interim phone vists 							

Subjects may be enrolled into the study at any time between the ages of 0-6 months and will receive TAVT-18 (sirolimus) until 12 months of age. Visit window for follow-up visits is  $\pm 2$  weeks.

Includes option for additional bloodwork for exploratory measures; subjects not taking study medication within the previous 48 hours of the study visit due to AE or other reasons will not have sirolimus level assessed.

Sirolimus trough levels should be drawn in the morning, approx. 24hrs after last dose of study medication. The initial level will be drawn 7-14 days after subject has been on steady dosing and in conjunction with safety labs at each clinic follow-up visit (1,3,6,9,12 mths). Similarly, trough levels will be drawn at 7-14 days after any dose modification, until target concentration is reached. For convenience, levels can be drawn at the study center or drawn locally and sent to the reference laboratory.

Routine EEG (60 minutes duration). EEG acquisition schedule for study is consistent with current TSC clinical guideline recommendations dMRI is 15-minute add-on sequence to conventional MRI that is recommended clinically every 1-3 years in TSC.

Developmental assessment consists of TAND Checklist, VABS, and Bayley-4 at the 12 months of Age visit and TAND Checklist, VABS, Bayley-4, PLS-5, and ADOS-2 at the 24 months of Age visit

Monthly calls will occur in between in-person visits. During the first month in the study, phone calls will occur weekly.

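### Inclusion criterion 1 cannot be met as printed: its corrected-age formula cannot give 39 weeks in an infant under 7 months old

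*Combined protocol and SAP*

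**What the plan says.** Criterion 1 in section 8.1 (Inclusion Criteria) combines an upper age limit with a minimum corrected age.

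- Upper limit: "subject must be <7 months of chronological age at time of randomization and treatment initiation".
- Minimum and its definition: "Corrected age must be at least 39 weeks (calculated by subtracting the number of weeks born before 40 weeks gestation from the chronological age").

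Corrected age is not defined anywhere else in the document.

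Other sections describe the population as newborns to six-month-olds:

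- Section 8: "Male and female TSC infants 0-6 months of age will be enrolled".
- Section 5: "Subjects will be between 0-6 months of age at time of treatment initiation".
- Section 11.5, baseline visit: "To be eligible, infants 0-6 months of age must have a confirmed diagnosis of TSC".
- Notes to Table 3: "Subjects may be enrolled into the study at any time between the ages of 0-6 months".
- Section 11.3 asks the DSMB whether the dose range is "appropriate for initial dosing in TSC infants 0-6 months of age".

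Section 9.1 gives a "starting dose based on age at the time of enrollment (see Table 2"), and the youngest band of Table 2 is 0-1 month. Section 11.5 also sets a phone-call schedule for infants who enrol at 0-3 months. Exclusion 5 in section 8.2 removes births before 30 weeks' gestation, so infants born at 30 weeks or later can still be candidates.

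**The concern.** The formula starts from chronological age and takes weeks away. The threshold it must reach, 39 weeks, is about nine months, which is above the upper age limit in the same criterion. The threshold, the formula and the limit cannot all hold.

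This matters because the text decides who may receive an investigational drug. Section 11.5 allows study drug to be dispensed only after eligibility is confirmed, and section 15.3 has the monitor check the eligibility of enrolled infants and the reporting of deviations. Read literally, every one of the five planned infants would fail an inclusion criterion.

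Setting the sentence aside leaves a gap at the lower end. It is the only place where the documents try to set a minimum age that takes prematurity into account. Section 3 itself notes that drug clearance in very young children can vary considerably while organ function is developing, so whether such a minimum exists, and what it is, has some substance.

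**Working it through.** **Inputs**

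- Upper limit on chronological age: under 7 months (section 8.1).
- Minimum corrected age: 39 weeks (section 8.1).
- Formula (section 8.1): corrected age = chronological age − max(0, 40 − GA), where GA is gestational age at birth in weeks.
- Earliest permitted birth: GA 30 weeks (section 8.2, exclusion 5).

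**Step 1: the upper limit in weeks.** Depending on the start date, seven calendar months last 212 to 215 days. 212/7 = 30.29 weeks and 215/7 = 30.71 weeks. The limit is strict, so these values are approached but not reached.

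**Step 2: highest corrected age and shortfall against 39 weeks.**

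| GA at birth | Weeks subtracted | Highest corrected age (weeks) | Shortfall (weeks) |
|---|---|---|---|
| 40 | 0 | 30.29 to 30.71 | 8.29 to 8.71 |
| 37 | 3 | 27.29 to 27.71 | 11.29 to 11.71 |
| 34 | 6 | 24.29 to 24.71 | 14.29 to 14.71 |
| 30 | 10 | 20.29 to 20.71 | 18.29 to 18.71 |

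**Step 3: chronological age at which the printed rule is first met.** This is 39 + max(0, 40 − GA) weeks. One month is 365.25/12/7 = 4.348 weeks.

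- GA 40: 39 weeks; 39/4.348 = 8.97 months.
- GA 30: 39 + 10 = 49 weeks; 49/4.348 = 11.27 months.

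Both are past the 7-month limit.

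**Step 4: a more generous reading.** Suppose weeks born after 40 weeks' gestation are added instead of ignored. With an average month, 7 months is 30.44 weeks, and a birth at 42 weeks gives 30.44 + 2 = 32.4 weeks, still below 39. Reaching 39 weeks would need a birth at 40 + (39 − 30.44) = 48.6 weeks' gestation.

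**Step 5: what the ambiguity does to one infant.** Take an infant born at 34 weeks and now 2 weeks old.

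- Printed formula: 2 − 6 = −4 weeks. Not eligible, like every other infant.
- Sentence disregarded as an error: the infant is within 0-6 months. Eligible on age.
- The 39 weeks read as gestational age at birth plus chronological age: 34 + 2 = 36 weeks. Not eligible.

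The third reading is an assumption for illustration, and the documents do not state it. Under it the criterion can be met: a birth at 30 weeks qualifies from 9 weeks of age, at 34 weeks from 5 weeks, at 37 weeks from 2 weeks, and at 39 weeks or later from birth.

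**The case against.** The best defence is that this is one mis-paired phrase and not a flaw in the design. The sentence already refers to 40 weeks' gestation, and if 39 weeks is counted from the start of gestation the rule works for every permitted birth. The intended 0-6 month range is plain throughout the protocol. The study is a pilot in five infants at a single site, and no endpoint, test, sample size or dose depends on the sentence. The documents do not show whether any of the five had already been enrolled under version 7.0, so an effect on future enrolment is not proven. On this view the point is minor.

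Much of that stands, and it limits the seriousness. It does not make the criterion usable. The gestational reading contradicts the formula printed in the same sentence, so adopting it means overriding the text. A clear 0-6 month range settles the upper end of eligibility but not the lower end for preterm infants.

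Other safeguards reduce the safety concern:

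- exclusion of illness or infection, neonatal complications that add risk of seizures or developmental delay, and clinically significant abnormal laboratory values (section 8.2);
- baseline safety laboratory results verified before the first dose (section 11.2);
- drug levels at 1, 3, 6 and 24 hours after the first dose (sections 9.1 and 11.2), and again around days 7 and 14.

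Section 11.2 also repeats safety laboratory tests at days 7 and 14, but Table 3 and the laboratory paragraph of section 11.6 do not list them, so that safeguard is itself inconsistently specified. None of these measures sets a minimum age.

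**Conclusion.** The concern holds. As printed, no infant can satisfy criterion 1. The gap is at least 8.3 weeks for a birth at 40 weeks and widens to at least 18.3 weeks for a birth at 30 weeks. The result rests only on the protocol's own formula, threshold and age limit plus calendar arithmetic, and crediting post-term weeks does not change it.

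The sentence should be corrected, although its practical reach is modest. Enrolment would probably proceed on the apparent intent, which is a judgement about site behaviour and not something the documents state. Nothing in section 16 is affected. What the documents leave undetermined is whether an age-based minimum applies to infants born preterm at 30 weeks or later and, if so, what it is.

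**What to change.** Amend criterion 1 so that the threshold and the formula are on the same named age scale, can be met below the 7-month limit, and agree with the 0-6 month range used in sections 5, 8, 9.1, 11.3 and 11.5. The sponsor has to choose the scale and the value; none is proposed here. The change is one sentence in a protocol amendment and needs no change to the analysis plan or sample size.

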## 8.2 Exclusion Criteria

- 1. Prior history of seizures (clinical or electrographic) at the time of enrollment or identified on baseline EEG
- 2. Has been treated in the past or is currently being treated at the time of enrollment with conventional anticonvulsant medications (AEDs), systemic (oral) mTOR inhibitors (such as rapamycin, sirolimus, or everolimus), ketogenic-related special diet, or another anti-seizure therapeutic agent, device, or procedure
- 3. Has taken any other investigational drug as part of another research study, within 30 days prior to the baseline screening visit
- 4. Has a significant illness or active infection at the time of the baseline screening visit
- 5. Has a history of significant prematurity, defined as gestational age <30 weeks at the time of delivery, or other significant medical complications at birth or during the neonatal period that other than TSC would convey additional risk of seizures or

neurodevelopmental delay (i.e. HIE, severe neonatal infection, major surgery, prolonged ventilatory or other life-saving supportive care or procedures)

- 6. Abnormal laboratory values at baseline (i.e., renal function, liver function, or bone marrow production) that are in the opinion of the investigator clinically significant and may jeopardize the safety of the study subject
- 7. Prior, planned or anticipated neurosurgery within 3 months of the baseline visit
- 8. Has a TSC-associated condition for which mTOR treatment is clinically indicated (i.e. SEGA or AML)
- 9. Subjects who are, in the opinion of the investigator, unable to comply with the requirements of the study

